## **7. STUDY PROCEDURES**

### **7.1 Screening**

The screening (Pre-cycle) period occurs within 28 days prior to Cycle 1, Day 1 of therapy. Please see Schedule of Study Procedures for additional details.

### **7.2 Treatment Period**

Clinical evaluations and laboratory assessments will be performed as per the Schedule of Study Procedures and as clinically indicated.

### **7.3 End of Treatment Visit**

Unless a patient withdraws consent for study participation or is lost to follow-up, an End-of-Treatment Visit is to occur 90 days after the last dose of study treatment, or as soon as possible before the start of subsequent therapy. Every effort should be made to conduct the End-of-Treatment Visit before the patient starts subsequent treatment. After last administration of treatment, patients will be monitored for 90 days to identify any late toxicities that may occur as a result of immunotherapy.

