### SCHEDULE OF STUDY PROCEDURES

Screening Phase  Day-28 to 0		Treatment	End of Treatm	Post-Treatment Observation Phase
		(Cycle is 28 days) +/- 3 days for Cycle 1 and 2, +/- 7 days for Cycles 3-30	At 1 year (+/- 7 days) & 90 days after last dose of study drug (+/-7 days)	Each cycle is 90 days, +/- 30 days for 24 months or until progression
Informed consent a	X			
Inclusion/exclusion criteria review	X			
Demography/Medical history	X			
Physical Exam	X	X b (every cycle)	X	
Vital signs c	X	X d (every cycle)	X	
Weight	X	X (every cycle)	X	
ECOG status	X	X (every cycle)	X	
ECG	X			
Echocardiogram	X		X	
Pulmonary function testing e	X e		X e	
Chest x-ray f				
NYHA classification	X	X (cycle 1 only)	X	
Patient Diary g	X	X (every cycle)	X	
Concomitant medications	Continuous from time of ICF until 30 days of last treatment			
Adverse events	Continuous from time of ICF until 30 days of last treatment			
Study Drug Administration				
Daratumumab 1800 mg SC dosing h		Daratumumab 1800 mg SC on Days 1, 8, 15, and 22 of Cycles 1 and 2 (weekly dosing), on Days 1 and 15 of Cycles 3 to 6 (every 2 weeks dosing), and on Day 1 of Cycle 7 and subsequent cycles (every 4 weeks dosing)		

Clarithromycin		500 mg PO bid continuous days 1-28 of cycles 1-8 only		
Pomalidomide		Pomalidomide 4 mg PO days 1-21		

Dexamethasone		Dexamethasone (Cycle 1 D1 & 8): 20 mg IV Cycle 1 D2 & D9: 20mg PO Cycle 1 D15 & D22: 40mg PO Cycles 2- 6: 40 mg PO qwk Cycles 7- 8: 20mg PO qwk Cycle 9+: 20mg PO qwk		
Prophylactic Medications				
Varicella Zoster Prophylaxis		Valacyclovir 500mg PO qd (or equivalent, renally dosed-adjusted)		
Gastrointestinal Prophylaxis		Pantoprazole 40 mg PO daily, or other		
Laboratory Assessments				
Pregnancy test i	X	X	X	
Blood typing/indirect antiglobulin test	X			
Hematology (CBC) with differential	X	On Days 1, 8, 15, and 22 for Cycles 1 and 2; On Days 1 and 15 for Cycles 3 through 6; D1 from Cycle 7 onward and as clinically indicated	X	
Serum chemistry j	X	On Days 1, 8, 15, and 22 for Cycle 1-2, Day 1, 15 for cycles 3-6 and day 1 of each subsequent cycle	X	
Hepatitis B and C screening k	X	HBV DNA monitoring q12weeks	X	X i
Disease Assessments				
Serum $\beta$ 2-microglobulin	X			
Serum free light chains	X	X (every cycle)	X	X (every cycle)

SPEP and IFE	X	X (every cycle)	X	X (every cycle)

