#### Follow-up

At the completion or early discontinuation of treatment, patients will be followed for an additional 90 days after the last administration of treatment or up until the initiation of the next line of treatment, whichever comes first. Patients with adverse events will be followed until the event has resolved or the condition has stabilized

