### 8.1.5 Safety Analysis

Safety parameters will include SAEs, TEAEs, physical examination findings (including ECOG performance status), vital sign measurements, standard clinical laboratory parameters (serum chemistry, hematology, urinalysis), and ECG parameters. Adverse events will be graded according to the NCI-CTCAE v4. The incidence of DLTs will also be evaluated.

Safety analyses in general will be descriptive and will be presented in tabular format with the appropriate summary statistics.

A TEAE is defined as an adverse event that emerges during the treatment period (from first dose date till 30 ( $\pm$  5) days after the last dosing date), having been absent at pre-treatment; or reemerges during treatment, having been present at baseline but stopped prior to treatment; or worsens in severity after starting treatment relative to the pre-treatment state, when the adverse event is continuous. The number and percentage of patients reporting TEAEs will be tabulated by the worst NCI-CTCAE grade, system organ class (SOC), and preferred term.

Similarly, the number and percentage of patients reporting treatment-emergent SAEs will be tabulated, as well as TEAEs/SAEs considered related to Daratumumab, Clarithromycin, Pomalidomide, and Dexamethasone.

A by-patient AE (including TEAE) data listing will be provided including, but not limited to, verbatim term, preferred term, SOC, NCI-CTCAE grade, and relationship to study drug.

Deaths, other SAEs, and other significant adverse events, including those leading to permanent discontinuation from Daratumumab, Pomalidomide, and Dexamethasone, will be listed.

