#### 9.2.1.1 Management of Safety Data

This Study has been designated as an interventional study. As such, all adverse events for Janssen Medicinal Products regardless of causality and special situations and product quality complaints with or without an adverse event as described in this Exhibit will be reported from the time a patient has signed and dated an Informed Consent Form (ICF) until completion of the patient's last study-related procedure (which may include contact for follow-up safety). Serious adverse events will be reported for 30 days after the last dose of study drug.

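### Patients are monitored for late toxicity to 90 days after the last dose, but the windows for recording, reporting and summarising adverse events contradict this and each other

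*Combined protocol and SAP*

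**What the plan says.** **Provisions that run to 90 days.** Section 7.3 sets the End-of-Treatment visit 90 days after the last dose, or earlier if needed to precede the next therapy, and gives the period a safety purpose: "patients will be monitored for 90 days to identify any late toxicities that may occur as a result of immunotherapy". The Follow-up paragraph of Section 4.3 agrees that "patients will be followed for an additional 90 days after the last administration of treatment", ending sooner if the next line of treatment begins. The calendar places the visit at the same time, with a tolerance of 7 days either way.

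**Provisions that stop at 30 days.** The AE row of the Schedule of Study Procedures reads "Continuous from time of ICF until 30 days of last treatment". Section 9.2.1.1 states: "Serious adverse events will be reported for 30 days after the last dose of study drug". Section 8.1.5 defines the treatment-emergent (TEAE) window as running "from first dose date till 30" (±5) days after the last dosing date.

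**A provision with no fixed end.** In the same paragraph of Section 9.2.1.1, all AEs for the supplying company's products, whatever their cause, are to be reported from consent "until completion of the patient's last study-related procedure (which may include contact for follow-up safety").

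**The concern.** The plan schedules a 90-day period in order to find late toxicity, but the documents a site and a programmer would work from do not carry that period through.

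- **Collection.** The calendar closes the AE row long before the visit that is meant to detect late events.
- **Reporting.** One paragraph of Section 9.2.1.1 gives serious events a shorter stated window than AEs in general, the reverse of what one would expect.
- **Analysis.** Nothing says how an event that starts after the TEAE window is to be summarised.

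Safety is a stated output of the trial: the secondary objectives in the Protocol Summary include AEs in the induction and maintenance phases. The regimen combines four drugs in a single arm of 40 patients with no control group. If sites resolve the contradiction differently, the completeness of late safety data will depend on which section each site followed.

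**Working it through.** The plan gives no figure on this point to reproduce. The check sets the windows side by side.

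| Provision | What it governs | Where it ends, counted from the last dose |
|---|---|---|
| Section 7.3 | Monitoring for late toxicity | 90 days, or before next therapy |
| Section 4.3, Follow-up | Patient follow-up | 90 days, or next line if earlier |
| Schedule, End of Treatment column | Visit | 90 ± 7 days |
| Schedule, AE row | AE collection | 30 days |
| Section 9.2.1.1, all-AE sentence | AEs for the company's product | Last study-related procedure |
| Section 9.2.1.1, SAE sentence | SAE reporting | 30 days |
| Section 8.1.5 | TEAE tables | 30 ± 5 days |

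**Step 1: length of the gap.** Gap = 90 − window.
- At 30 days: 90 − 30 = 60 days, and 60/90 = 67%.
- At 35 days (upper TEAE tolerance): 90 − 35 = 55 days, and 55/90 = 61%.
- At 25 days (lower TEAE tolerance): 90 − 25 = 65 days, and 65/90 = 72%.

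**Step 2: distance from the close of collection to the visit.** The visit may fall on days 83 to 97 (90 − 7 to 90 + 7). That is 83 − 30 = 53 to 97 − 30 = 67 days after the AE row has closed.

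**Step 3: the gap under the all-AE sentence.** For a patient who attends the day-90 visit, the last study procedure cannot be earlier than that visit, so the reporting gap is 0 days. For a patient who goes on to post-treatment observation, with disease evaluations for up to 24 months, the end could be later still. The two rules for AEs therefore differ by at least 60 days for a patient seen on day 90.

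**Step 4: a new event with onset on day 60.**
- Calendar: not collected.
- Section 9.2.1.1, all-AE sentence: reportable.
- Section 9.2.1.1, SAE sentence: if the event is serious, outside the stated period.
- Section 8.1.5, TEAE tables and treatment-emergent SAE tables: excluded.
- Section 8.1.5, by-patient AE listing: can appear, because the listing is not restricted to TEAEs, but only if a site recorded the event.

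One event thus receives conflicting instructions on collection and reporting, and no planned summary.

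**The case against.** The strongest reply is that the plan has several routes by which a late event is captured.

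- The all-AE sentence in Section 9.2.1.1 covers days 31 to 90 for anyone who attends the day-90 visit. It applies regardless of causality.
- Section 9.2.1.7 has all AEs after exposure to the company's product recorded in the CRF, with no 30-day limit.
- Section 9.1.2 makes any death an SAE. Section 9.2.1.2 sends events of special interest, including grade 4 or higher infections and cytopenias, to the company within 24 hours. Section 9.2.2 requires notice to the IRB within 7 days of learning of an SAE. None of these states a window.
- Footnote k of the calendar continues HBV DNA testing for up to 6 months in patients with positive serology.
- A serious AE is still an AE, so the 30-day sentence may be meant to limit only SAE-specific reporting.

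Much of this stands, and it rules out three stronger conclusions that a reader might draw.

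1. *Late events would not be counted at all.* The all-AE sentence and the unrestricted listing contradict this.
2. *Serious late events drop out of reporting.* The routes above remain open, and Section 9.2.1.1 is ambiguous rather than a clear exclusion.
3. *The hold for grade 3-4 infections above 15% would miss late infections.* Section 8.1.7 gives that rule no time window, no denominator and no link to the TEAE definition, so the documents do not say whether late infections count.

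The 30-day TEAE definition is also not an error in itself.

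The reply does not remove the contradiction. The all-AE sentence is worded for the company's product and does not clearly govern the other three drugs. It also conflicts with the calendar. A listing shows only what was recorded and is not a summary. Following existing AEs to resolution, as Section 4.3 requires, does not open a window for new ones.

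**Conclusion.** The point holds as an internal contradiction, and this is certain from the text. Monitoring for late toxicity runs to 90 days, AE collection in the calendar and SAE reporting stop at 30, and the all-AE rule runs to the last procedure. Events with onset after the TEAE window would at best be listed and not summarised.

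The mismatch is up to 60 of 90 days (67%), or 55 to 65 days (61% to 72%) against the TEAE window. This is a maximum, because the 90-day period ends early for a patient who starts new therapy. It measures time and not events: the documents give no rate of toxicity for days 31 to 90, so the number of events affected cannot be estimated.

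The practical consequence assumes that sites take their collection rules from the calendar. The primary endpoint is unaffected. The correction should be made because safety is a stated output and the visit needed for it is already scheduled.

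**What to change.** 1. In the calendar's AE row and in Section 9.2.1.1, collect AEs and SAEs, for all four drugs, through the 90-day End-of-Treatment visit or the start of next therapy, whichever is first. State one window for both, and say separately whether any reporting to the company continues beyond it.
2. Keep the 30 (±5) day TEAE definition in Section 8.1.5 and its tables.
3. Add to Section 8.1.5 a separate summary of events with onset after the TEAE window and up to day 90, by grade and seriousness.

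The cost is a wording change in two places, one added table and slightly more event reporting. No new visit is needed.

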### **7.4 Post-Treatment Observation Phase**

For patients who complete all 32 cycles of treatment on study, if have not progressed or started new treatment, patients will be followed with disease evaluations every 90 days (+/- 30 days) until confirmed disease progression or for total duration of 24 months from last EOT visit, whichever comes first, and for OS for up to 10 years from date of enrollment or until death.

Patients who discontinue study treatment before disease progression has been observed, will undergo disease evaluations every 90 days (+/- 30 days) as specified in the Post-Treatment Observation Phase in the Study Calendar for a duration of 24 months or until confirmed hematologic disease progression, whichever comes first.

### **7.5 High-Dose Chemotherapy and Autologous Stem Cell Transplantation**

Patients may undergo stem cell collection while on study. Mobilization agents can include granulocyte colony stimulating factor or plerixafor. Additional cyclophosphamide is permitted for chemotherapy-based mobilization. While undergoing stem cell collection, patients may hold their study treatment for a maximum of 4 weeks and should thereafter continue on treatment as per study protocol.

Patients who undergo high-dose chemotherapy and ASCT following 6 cycles of therapy after the secondary endpoint of overall hematologic response is assessed will be removed from study protocol. They will remain though in the Post-Treatment Observation phase for 24 months and undergo disease evaluations every evaluations every 90 days (+/- 30 days) as

specified in the Post-Treatment Observation Phase in the Study Calendar for a duration of 24 months or until confirmed hematologic disease progression, whichever comes first.

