## **3. STUDY ENDPOINTS**

### **3.1 Primary Endpoints**

- $\geq$  VGPR response proportion as best response within 8 cycles of induction treatment

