#### **6.4 Excluded Concomitant Medications and Procedures**

The following medications and procedures are prohibited during the study.

Systemic treatment with concurrent drugs known to prolong the QT interval (see Appendix 12.3)

Systemic treatment with any of the following metabolizing enzyme inducers should be avoided, unless there is no appropriate alternative medication for the patient's use:

- Strong CYP3A inducers: rifampin, rifapentine, rifabutin, carbamazepine, phenytoin, and phenobarbital. For a more comprehensive list of CYP3A inducers, please refer to Appendix 12.4.

The following medicinal products and procedures are prohibited during the study.

- Excluded foods and dietary supplements include St. John's wort and Ginkgo biloba.
- Any antineoplastic treatment with activity against MM, other than study drugs
- Radiation therapy (note that, in general, the requirement for local radiation therapy indicates disease progression)
- Platelet transfusions to help patients meet eligibility criteria are not allowed within 3 days prior to study drug dosing for any dosing day

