## 8. STATISTICAL AND QUANTITATIVE ANALYSES

### 8.1 Statistical Methods

The primary endpoint will be the  $\geq$  VGPR response proportion as best response within the first 8 cycles of treatment. Based on historical data, the  $\geq$  VGPR response proportion is approximately 9%; therefore, the target  $\geq$  VGPR response proportion will be  $\geq$  25%.

This exact single-stage design yields a  $\geq$  0.80 probability of a positive result if the true  $\geq$  VGPR response proportion is  $\geq$  25%. It yields a  $\geq$  0.95 probability of a negative result if the true  $\geq$  VGPR response proportion is  $\leq$  9%. A 95% confidence interval constructed around the expected  $\geq$  VGPR response proportion of 25% can be estimated to be within  $\pm$  17.9% of the observed  $\geq$  VGPR response proportion.

Analysis Plan for Endpoints:

Primary Endpoint:

The primary endpoint is the  $\geq$  VGPR response proportion as best response within the first 8 cycles of treatment; A 95% confidence interval will be estimated for the  $\geq$  VGPR response proportion via binomial proportions.

Secondary endpoints:

Secondary endpoints include median PFS, OS, time to response and progression, DoR, TTNT, ORR, VGPR rate, CR or better rate, improvement in response rate during maintenance therapy and MRD negativity rate. Median PFS/OS, including survival curves, will be estimated using Kaplan-Meier methodology. Greenwood's formula will be used to calculate 95% confidence intervals for the Kaplan-Meier survival estimates.

All analyses will be performed in SAS Version 9.4 (SAS Institute, Inc., Cary, North Carolina) and Stata Version 15.0 (StataCorp, College Station, Texas).

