#### 8.1.1 Determination of Sample Size

The sample size computations were performed assuming a 5% level of significance and 80% power. The new regimen will be declared effective and worthy of further testing if 8 or more patients have  $\geq$  VGPR among the 40 patients entered into the cohort.

Sample size recommendations for the current design are determined according to A'Hern's exact single-stage phase II design (A'Hern, RP, 2001). We project a  $\geq$  VGPR response proportion of 9%, below which the regimen will be unacceptable, and a  $\geq$  VGPR response proportion of 25%, above which the regimen will be considered worthy of further exploration. The null hypothesis that the  $\geq$  VGPR response proportion is less than or equal to 9% will be tested against the alternative hypothesis that the  $\geq$  VGPR response proportion is greater than or equal to 25%.

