##### Response

Parameters assessed will include stringent complete response (sCR), complete response (CR), very good partial response (VGPR), partial response (PR), and stable disease (SD) per standard IMWG response criteria. In addition, overall response rate (defined as greater than or equal to PR across all cycles of treatment), response duration, time-to-response (TTR), MRD negativity rate and improvement in response during maintenance therapy will be assessed.

Best overall response categories will be tabulated and overall for CR, VGPR, PR, SD, progressive disease, and relapse. A two-sided 95% exact binominal CI will be calculated for each category. The response rate (responses  $\geq$  PR) will also be tabulated. Time-to-event analyses will be done using Kaplan- Meier analyses and will include time to response, duration of response, PFS, and OS, as data allow. If there is not enough data to apply the Kaplan-Meier test, the data will be summarized by descriptive statistics.

Time to response (for responders only) will be calculated as the time from the date of first study treatment dosing to the first date of documented response (PR or better) and will be summarized by descriptive statistics.

Duration of response (for responders only) is defined as the time from the earliest date of documented response (PR or better) to the earliest date when disease progression was confirmed. Patients who are non-responders will be excluded from this analysis. Detailed censoring rules for duration of response will be specified in the SAP.

PFS will be calculated as the time from the initial administration of Daratumumab, Clarithromycin, Pomalidomide, and Dexamethasone until documented disease progression, as determined using standard response criteria, or death from any cause, whichever occurs first. Kaplan-Meier methods will be used to estimate PFS over time and the median duration of PFS. Patients with no PFS event will be censored at the date of their last disease assessment.

Time to next therapy is defined as the time from the initial administration of Daratumumab, Clarithromycin, Pomalidomide, and Dexamethasone on trial to next treatment.

OS is defined as the time from the initial administration of Daratumumab, Clarithromycin Pomalidomide and Dexamethasone to death from any cause. Kaplan-Meier methods will be used to estimate the OS function. Patients who do not die will be censored at the date that the patient was last known to be alive.

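### Cyclophosphamide mobilisation is allowed on study with no response cut-off, so a VGPR reached only after it counts as a D-ClaPd success

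*Combined protocol and SAP*

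**What the plan says.** Section 7.5 lets patients collect stem cells while on study. Growth factor and plerixafor are listed as mobilising agents, and "Additional cyclophosphamide is permitted for chemotherapy-based mobilization". No cycle restriction is given. Study treatment may be held for up to 4 weeks and then continues.

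Section 6.4 lists among the prohibited items "Any antineoplastic treatment with activity against MM, other than study drugs". It makes no exception for mobilisation.

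The primary endpoint in Section 3.1 is the ≥ "VGPR response proportion as best response within 8 cycles of induction treatment". Section 8.1 repeats it as the "response proportion as best response within the first 8 cycles of treatment". Neither section says how a response first seen after non-study chemotherapy is classified.

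On transplant, Section 7.5 refers to "Patients who undergo high-dose chemotherapy and ASCT following 6 cycles of therapy after the secondary endpoint of overall hematologic response is assessed". Such patients are removed from the study protocol but stay in disease evaluation every 90 days for 24 months or until progression. Exclusion criterion 5 in Section 5.2 bars only transplant planned within the first 6 cycles.

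Section 8.1.6 measures PFS to progression or death. Its only censoring rule is "Patients with no PFS event will be censored at the date of their last disease assessment". For duration of response, the same section leaves the detailed censoring rules to the SAP.

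**The concern.** The trial has one arm and a fixed historical reference, so everything that deepens a response during the window is credited to the regimen. Cyclophosphamide cannot be assumed inert: the protocol's own table of daratumumab studies (Section 1.3.2) lists Dara-CyBorD in newly diagnosed and relapsed myeloma, and the text on subcutaneous combination therapy spells out CyBorD as including cyclophosphamide. A patient in PR who is mobilised with cyclophosphamide in, say, cycle 5, resumes study drugs and shows VGPR in cycle 6 is a success under the plan as written.

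What is at stake is the go decision. The rule is 8 or more of 40, so the difference between 7 and 8 rests on one patient.

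A second mismatch is that the transplant milestone in Section 7.5 and exclusion 5 both stop at 6 cycles, while the primary window runs to 8. A third is that post-transplant remission time enters PFS as defined. It could then be read against the benchmarks in Section 1.1 (median PFS about 4 months for pomalidomide/dexamethasone and 7.7 months for ClaPd).

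**Working it through.** **Inputs from the documents.** N = 40 and success at 8 or more responders (Section 8.1.1). The null is p0 = 0.09: Section 8.1 says the historical ≥VGPR "response proportion is approximately 9" per cent. The target is p1 = 0.25: Section 8.1.1 gives a "response proportion of 25%, above which the regimen will be considered worthy of further exploration". The stated significance level is 5% and power 80%. The test is taken as a one-sided exact binomial test, as in A'Hern's design.

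**Step 1: reproduce the plan.**
- P(X ≥ 8 | n = 40, p = 0.09) = 0.0242, below 0.05.
- P(X ≥ 8 | n = 40, p = 0.25) = 0.8180, above 0.80.
- A cut-off of 7 would give P(X ≥ 7 | n = 40, p = 0.09) = 0.0639, so 8 is the smallest valid cut-off at N = 40.

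The design reproduces.

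**Step 2: effect given m misattributed responders.** Suppose m patients are scored ≥VGPR only because of non-study chemotherapy and the other 40 − m respond at the regimen's own rate p. Then P(go) = P(X ≥ 8 − m | n = 40 − m, p).

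| m | p = 0.09 | p = 0.15 |
|---|---|---|
| 0 | 0.024 | 0.244 |
| 1 | 0.057 | 0.367 |
| 2 | 0.122 | 0.515 |

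The column at 15% illustrates a true rate between null and target. At the null, one such patient takes the error above the stated 5%.

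**Step 3: allow for the chance that it happens.** Let f be the share of patients exposed to mobilising chemotherapy in the window, and c the probability that an exposed patient otherwise below VGPR is converted. The apparent rate is 0.09 + 0.91 × f × c, and P(go) = P(X ≥ 8 | n = 40, that rate). Both f and c are assumptions.

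| f | c | Apparent rate | P(go) |
|---|---|---|---|
| 5% (2 of 40) | 25% | 0.1014 | 0.045 |
| 5% (2 of 40) | 50% | 0.1128 | 0.075 |
| 10% (4 of 40) | 25% | 0.1128 | 0.075 |
| 10% (4 of 40) | 50% | 0.1355 | 0.166 |

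At the lowest of these settings the error stays under 5%; at the others it does not.

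**Step 4: bound the cost of a stricter count.** If every exposed patient were scored a non-responder, the rate under the target would be 0.25 × (1 − f). With f = 5% this is 0.2375, and P(X ≥ 8 | n = 40) = 0.767. With f = 10% it is 0.225, giving 0.706. These are worst cases, because the rule proposed here keeps any VGPR documented before the exposure.

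**Step 5: transplant and the time-to-event endpoints, from the text.** A patient transplanted after cycle 6 has left protocol treatment, so on a natural reading a later VGPR is not within 8 cycles of treatment. Losing cycles 7-8 also removes time in which VGPR could have been reached on study drugs. The text settles neither point. For PFS, follow-up continues after transplant and no rule censors at new therapy, so the time counts. For duration of response, the definition runs to confirmed progression but the censoring rules are not yet given.

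**The case against.** Several counter-arguments have force.

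- **The chain of events is long.** A patient must be mobilised within cycles 1-8, with cyclophosphamide rather than only growth factor or plerixafor, be below VGPR at that moment, and reach VGPR only because of it. No passage gives a conversion rate. This stands: 0.057 and 0.122 are conditional on the event having happened, which is why the range in Step 3 belongs beside them.
- **Section 7.5 may be a specific permission that overrides the general ban in Section 6.4.** That is possible, but it would settle only whether the drug may be given, not how the later response is scored.
- **PFS regardless of later therapy is a recognised definition.** This stands. Censoring at transplant is not neutral either, because Section 4.3 links leaving treatment for transplant to the level of response achieved, so such censoring may be informative. TTNT is already a secondary endpoint.

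A reader might infer that post-transplant responses also inflate the ≥VGPR rate. The documents do not support that: transplanted patients are removed from protocol, and the net effect may be downward. A reader might also infer that the plan has decided to count post-transplant time in duration of response. It has not; Section 8.1.6 defers those rules.

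**Conclusion.** The point holds for cyclophosphamide and the primary endpoint. Followed as written, the plan can credit a chemotherapy-deepened VGPR to D-ClaPd, and the decision rule has room for none at the stated 5% level: P(go) at a true 9% is 0.024 with no such patient, 0.057 given one and 0.122 given two. Under the assumed exposure of 5-10% and conversion of 25-50% it is 0.045-0.166, so a breach of 5% is plausible but not certain. The number of patients affected is not in the documents.

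For transplant, the defect is that the plan is silent about cycles 7-8; the direction of any bias in the ≥VGPR rate is unclear. PFS includes post-transplant time by definition, which is a defensible choice that needs a companion analysis; its effect on the median is not quantified here. Duration of response is an open gap. Confidence is medium.

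**What to change.** 1. In Sections 3.1 and 8.1.6, count a response toward ≥VGPR and the other response rates only if it is documented before the first mobilising chemotherapy, transplant conditioning or other non-protocol anti-myeloma therapy. Keep all such patients in the denominator; one without ≥VGPR by then is a non-responder for the primary endpoint.
2. Keep PFS as defined. Add a sensitivity analysis of PFS, TTP and duration of response censored at the last assessment before such therapy, and state that this censoring may be informative. Write the deferred duration-of-response rules accordingly.
3. The sponsor should reconcile Section 6.4 with Section 7.5, and the 6-cycle milestone in Section 7.5 and exclusion 5 with the 8-cycle window. Which clinical rule is right is not judged here.

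The cost is protocol and SAP wording and one derived date per patient; N and the cut-off of 8 do not change. The observed ≥VGPR rate may be slightly lower, and some power is lost. The worst-case bound at 5% exposed is 0.767, against 0.818 as planned; the actual loss is smaller because earlier VGPRs are kept. If nobody is mobilised with chemotherapy, transplanted or given other non-protocol therapy, nothing changes.
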